- ^e BSA will be measured as the affected BSA for each side of each hand. Affected areas of the lateral aspects of the fingers and hands should be assigned to the palmar surface. IGA will be a 5-point scale ranging from clear (0) to severe (4). **IGA should be completed prior to other physician assessments and by the same Evaluator at each study visit.** HECSI is an instrument used in clinical trials to rate the severity of 6 clinical signs of hand eczema and the extent of the lesions on each of 5 distinct hand anatomic areas by use of standard scales. The total HECSI score is based on a 4-point clinical sign severity scale ranging from 0 (none/absent) to 3 (severe) and a 5-point scale rating the different affected hand anatomic area(s) ranging from 0 (0% affected area) to 4 (76% to 100% affected area).
- ^f Subjects will complete the WI-NRS pruritis assessment and NRS Pain assessment in the clinic during screening and then daily at home from the Baseline/Day 1 visit through the Day 15 visit.
- ^g A serum pregnancy test will be administered to all females of child-bearing potential at Screening. A urine pregnancy test will be administered at Visits 2, 4, 5, and 7 to all females of childbearing potential. A negative result is required for continued participation in the study, and results must be available prior to dispensing of investigational product.
- ^h FSH will be performed (if indicated) at Screening to confirm post-menopausal status.
- ⁱ On the first day of dosing (Day 1), PK samples will be collected at 1, 2, 4, 6 (all +/- 10 mins) and 24 hours post-dose administration (Day 2, +/- 2 hours). On Day 15 (last dose application), PK samples will be collected pre-dose, 1, 2, 4, 6, (all +/- 10 mins) and 24 hours post dose administration (Day 16, +/- 2 hours). For 24-hour timepoints, subjects return to the clinic on the following day within 2 hours of the IP application time from the previous day for pre-dose PK plasma sample. A pre-dose PK sample will be taken at Day 8.
- ^j Clinic personnel will apply assigned IP on Visits 2, 4 and 5 (Baseline, Day 8 and Day 15). Every tube should be weighed before and after IP application and weights recorded. For the 24-hour PK sampling timepoint the application of investigational product should occur after the PK sample has been collected.
- ^k Subject should return with investigational product kit at each Visit. Every tube should be weighed before and after use and weights recorded when dispensed and returned.

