4.12.2 Treatment Administration

Initial treatment with the IP will occur on Day 1. At the Baseline visit the study staff will demonstrate to the subject how to apply IP using the first tube that is assigned to the subject at enrollment/randomization. Study site staff will demonstrate how two unit doses (two pea size amounts of IP will cover approximately 4% BSA, i.e., both hands entirely) are properly squeezed from the tube and applied as a thin film to cover both hands. IP will be applied to the front and back of both hands, interlacing fingers, rubbing in thoroughly but gently, until the cream has absorbed. The subject will then practice squeezing a similar amount and applying IP. The study staff will confirm that the subject's application technique is correct.

Subjects in Cohort 1 will be instructed to apply IP once daily (QD). Subjects in Cohort 2 will be instructed to apply IP either once daily (QD) or twice daily (BID), as determined at randomization.

IP tubes must be returned by subjects at each study visit, both empty and full, and will be weighed. Re-training will be conducted at subsequent visits as needed (i.e., if the returned tube weighs substantially different than the expected weight).

Subjects will be instructed to refrain from handwashing for 4 hours after IP application, if possible. Subjects may use hand sanitizer within 4 hours of IP application, if necessary. Hand washing and use of hand sanitizer within 4 hours of IP application will be recorded in the subjects' diary and CRF.

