- i On the first day of dosing (Day 1), PK samples will be collected at 1, 2, 4, 6 (all +/- 10 mins) and 24 hours post-dose administration (Day 2, +/- 2 hours). On Day 15 (last dose application), PK samples will be collected pre-dose, 1, 2, 4, 6, (all +/- 10 mins) and 24 hours post dose administration (Day 16, +/- 2 hours). For 24-hour time points, subjects return to the clinic on the following day within 2 hours of the IP application time from the previous day for pre-dose PK plasma sample. A pre-dose PK sample will be taken at Day 8.
- j Clinic personnel will apply assigned IP on Visits 2, 4 and 5 (Baseline, Day 8 and Day 15). Every tube should be weighed before and after IP application and weights recorded. For the 24-hour PK sampling time point the application of investigational product should occur after the PK sample has been collected.
- k Subject should return with investigational product kit at each Visit. Every tube should be weighed before and after use and weights recorded when dispensed and returned.
- l Any emergent AEs will be followed in the clinic for up to 1 month at the Investigator's discretion until resolved or otherwise judged as clinically stable

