- **Number of Expected IP Applications (BID dosing)** = 170 (Cohort 2 BID) for subjects who complete the study or number of days between first and last application of IP, derived as  $2 * (\text{last treatment date} - \text{first treatment date} + 1)$ , for subjects who discontinue early from the study.
- **Number of Expected IP Applications (QD dosing)** = 30 (Cohort 1) or 85 (Cohort 2 QD) for subjects who complete the study or number of days between first and last application of IP, derived as  $(\text{last treatment date} - \text{first treatment date} + 1)$ , for subjects who discontinue early from the study.
- **Number of IP Applications** = number of expected IP applications – missed IP applications as collected in the electronic case report form (eCRF).
- **Weight of IP (g)** = returned tube weight – dispensed tube weight.
- **Body Mass Index (BMI) ( $\text{kg}/\text{m}^2$ )** =  $[\text{weight (kg)} / \text{height (cm)} / \text{height (cm)}] \times 10,000$ .
- **Change from Baseline** = value at current time point – value at baseline.
- **Treatment Emergent AE (TEAE)** = any AE with an onset date/time after the first application of IP. If time is unavailable, any AE occurring on or after the date of first application of IP will be considered treatment emergent.
- **Completion of Study** = Completion of the primary efficacy assessment (IGA) at Week 12. This may differ than what was recorded in the eCRF.

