Note: Percentages are n/Number of subjects in the Safety population within treatment received\*100. Medications were coded using WHO-DDE Global B3 version September 2019. Prior medications are all medications that were started before the application of study drug. Medications are displayed by alphabetical order of ATC Level 4 classification, then descending frequency of PT within ATC, and then alphabetically by PT. Subjects were counted only once for each ATC and PT.

[1] ATC Level 4 was not definable for these preferred terms due to multiple ingredients that cannot be mapped to an ATC Level 4 term, route of administration and indication that is not defined in an ATC Level 4 term, or some similar circumstance.  
Reference Listing: 16.2.9.7

**Programming note:** ATC & PT text should be presented as is from the dataset. If medications are coded but are missing ATC Class Level 4, display as "NOT DEFINED [1]" in the ATC Class Level 4 row and include footnote [1]; otherwise remove footnote [1] from the table.

Table 14.1.6  
Cohorts 1 and 2: Summary of Study Drug Exposure and Compliance  
Safety Population

Variable Statistic / Category	Cohort 1					Cohort 2		
	ARQ-252 Cream 0.3% QD (N=XX)	ARQ-252 Cream 0.3% QD (N=XX)	ARQ-252 Cream 0.3% BID (N=XX)	ARQ-252 Cream 0.1% QD (N=XX)	Vehicle Cream QD (N=XX)	Vehicle Cream BID (N=XX)		
Total Number of IP Applications								
n	XX	XX	XX	XX	XX	XX		
Mean (SD)	XX.X (XX.XX)	XX.X (XX.XX)	XX.X (XX.XX)	XX.X (XX.XX)	XX.X (XX.XX)	XX.X (XX.XX)		
Median	XX.X	XX.X	XX.X	XX.X	XX.X	XX.X		
Min, Max	XX, XX	XX, XX	XX, XX	XX, XX	XX, XX	XX, XX		
Total Weight of IP Applied (g) [1]								
n	XX	XX	XX	XX	XX	XX		
Mean (SD)	XX.X (XX.XX)	XX.X (XX.XX)	XX.X (XX.XX)	XX.X (XX.XX)	XX.X (XX.XX)	XX.X (XX.XX)		
Median	XX.X	XX.X	XX.X	XX.X	XX.X	XX.X		
Min, Max	XX, XX	XX, XX	XX, XX	XX, XX	XX, XX	XX, XX		
Compliance [2]								
>100%	XX (XX.X%)	XX (XX.X%)	XX (XX.X%)	XX (XX.X%)	XX (XX.X%)	XX (XX.X%)		
≥ 80% - ≤100%	XX (XX.X%)	XX (XX.X%)	XX (XX.X%)	XX (XX.X%)	XX (XX.X%)	XX (XX.X%)		
< 80%	XX (XX.X%)	XX (XX.X%)	XX (XX.X%)	XX (XX.X%)	XX (XX.X%)	XX (XX.X%)		
> 3 Consecutive Missed Days	XX (XX.X%)	XX (XX.X%)	XX (XX.X%)	XX (XX.X%)	XX (XX.X%)	XX (XX.X%)		
Compliant [3]	XX (XX.X%)	XX (XX.X%)	XX (XX.X%)	XX (XX.X%)	XX (XX.X%)	XX (XX.X%)		

Abbreviations: BID = twice daily; IP = investigational product; QD = once daily.

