Note: n is the number of subjects in the Safety Population. Percentages are n/Number of subjects in the Safety Population within treatment received\*100.

[1] Total weight of IP is determined by subtracting returned tube weight from the dispensed tube weight.

[2] Compliance is calculated based on number of applications divided by the expected number of IP applications for each subject\*100.

[3] A subject is considered compliant if the subject applies at least 80% of the expected applications during the IP application period and does not miss more than 3 consecutive days of dosing (3 doses for QD and 6 doses for BID).

Reference Listings: 16.2.5.1, 16.2.5.2, 16.2.5.4

Table 14.2.1.1.1  
Cohort 2: Summary of Investigator Global Assessment (IGA) Grades and Score of “Clear” or “Almost Clear” by Study Visit – Multiple Imputation  
Categorical Results  
ITT Population

Study Visit Category/Statistic	Cohort 2				Vehicle Cream (All Dose Frequencies) (N=XX)
	ARQ-252 Cream 0.3% QD (N=XX)	ARQ-252 Cream 0.3% BID (N=XX)	ARQ-252 Cream 0.1% QD (N=XX)		
Baseline	XX	XX	XX	XX	XX
0 = Clear	XX (XX.X%)	XX (XX.X%)	XX (XX.X%)	XX (XX.X%)	XX (XX.X%)
1 = Almost Clear	XX (XX.X%)	XX (XX.X%)	XX (XX.X%)	XX (XX.X%)	XX (XX.X%)
2 = Mild	XX (XX.X%)	XX (XX.X%)	XX (XX.X%)	XX (XX.X%)	XX (XX.X%)
3 = Moderate	XX (XX.X%)	XX (XX.X%)	XX (XX.X%)	XX (XX.X%)	XX (XX.X%)
4 = Severe	XX (XX.X%)	XX (XX.X%)	XX (XX.X%)	XX (XX.X%)	XX (XX.X%)
Week 2	XX	XX	XX	XX	XX
0 = Clear	XX (XX.X%)	XX (XX.X%)	XX (XX.X%)	XX (XX.X%)	XX (XX.X%)
1 = Almost Clear	XX (XX.X%)	XX (XX.X%)	XX (XX.X%)	XX (XX.X%)	XX (XX.X%)
2 = Mild	XX (XX.X%)	XX (XX.X%)	XX (XX.X%)	XX (XX.X%)	XX (XX.X%)
3 = Moderate	XX (XX.X%)	XX (XX.X%)	XX (XX.X%)	XX (XX.X%)	XX (XX.X%)
4 = Severe	XX (XX.X%)	XX (XX.X%)	XX (XX.X%)	XX (XX.X%)	XX (XX.X%)
IGA Score of “Clear” or “Almost Clear” [1]					
Yes	XX (XX.X%)	XX (XX.X%)	XX (XX.X%)	XX (XX.X%)	XX (XX.X%)
90% CI [2]	(X.XX, X.XX)	(X.XX, X.XX)	(X.XX, X.XX)	(X.XX, X.XX)	(X.XX, X.XX)
95% CI [2]	(X.XX, X.XX)	(X.XX, X.XX)	(X.XX, X.XX)	(X.XX, X.XX)	(X.XX, X.XX)
No	XX (XX.X%)	XX (XX.X%)	XX (XX.X%)	XX (XX.X%)	XX (XX.X%)
Odds Ratio (90% CI) [3]	X.XX (X.XX, X.XX)	X.XX (X.XX, X.XX)	X.XX (X.XX, X.XX)	X.XX (X.XX, X.XX)	X.XX (X.XX, X.XX)
Odds Ratio (95% CI) [3]	X.XX (X.XX, X.XX)	X.XX (X.XX, X.XX)	X.XX (X.XX, X.XX)	X.XX (X.XX, X.XX)	X.XX (X.XX, X.XX)
P value [3]	X.XXXXX	X.XXXXX	X.XXXXX	X.XXXXX	X.XXXXX

*Continue for Weeks 4, 8, 12, and 13.*

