		XXXXXX	XXXXXX	Yes	DDMMYYYY (X)	XXXXXX	No	XXXXXXXXXXXX		
XXXXXX	XXXXXX	XXXXXX	XXXXXX	No	XXXXXX	XXXXXX	No	XXXXXXXXXXXX	DDMMYYYY (X)	

Abbreviations: BID = twice daily; QD = once daily.

Note: Study day is calculated relative to the date of first application of study drug.

[1] Treatment received for both cohorts.

Listing 16.2.5.4  
 Compliance (CRF)  
 All Subjects

Cohort: Cohort x

Subject ID	Treatment [1]	Study Visit [2]	Subject Compliant with Medication? [2]	Non-Compliance due to COVID-19? [2]	Date of Compliance Check (Study Day) [2]	Compliance [2]	Overall Compliance [3]		Was Subject Retained if not Compliant with Medication [2]
							[3]	[2]	
XXXXXX	XXXXXX	XXXXXX	XXX	XXX	DDMMYYYY (X)	XX.X %	XX.X %		
		XXXXXX	XXX	XX	DDMMYYYY (X)	XX.X %			
		XXXXXX	XXX	XX	DDMMYYYY (X)	XX.X %			
XXXXXX	XXXXXX	XXXXXX	XXX	XXX	DDMMYYYY (X)	XX.X %	XX.X %		
		XXXXXX	XXX	XX	DDMMYYYY (X)	XX.X %			
		XXXXXX	XX	XX				XXX	

Abbreviations: BID = twice daily; COVID-19 = novel coronavirus disease-19; CRF = case report form; IP = investigational product; QD = once daily.

Note: Study day is calculated relative to the date of first application of study drug.

[1] Treatment received for both cohorts.

[2] This data comes from CRF page and was only collected for subjects in Cohort 2.

[3] Overall compliance will be calculated based on number of applications divided by the expected number of IP applications for each subject. For BID dosing, the expected number of IP applications for each subject is 30 (Cohort 1) or 170 (Cohort 2 BID) for subjects who completed the study or number of days between first and last application of IP, derived as 2 \* (last treatment date - first treatment date + 1), for subjects who discontinued early from the study. For QD dosing, the expected number of IP applications for each subject is 85 (Cohort 2 QD) for subjects who completed the study or number of days between first and last application of IP, derived as (last treatment date - first treatment date + 1), for subjects who discontinued early from the study. Number of IP applications is calculated as number of expected IP applications – missed IP applications as collected in the CRF.

**Programming note:** Populate overall compliance only for the first visit.

Listing 16.2.5.5.1  
 Study Drug Interruption (QD)  
 All Subjects

Subject ID	Treatment [1]	Study Visit	Missed Dose (Study Day)	Date of Missed Dose due to COVID-19 Disruption?	Reason for Missed Dose

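### SAP 6.1.7 expects 30 applications from a Cohort 1 completer, but once-daily use from Day 1 to Day 15 gives 15; the tube-weight formula is also reversed

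*SAP*

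**What the plan says.** **The constant.** On its once-daily line, SAP 6.1.7 (Derived Variables) gives the expected number of applications as "30 (Cohort 1) or 85 (Cohort 2 QD) for subjects who complete the study". Subjects who leave early get last treatment date minus first treatment date plus one. The twice-daily line gives 170 for Cohort 2 completers and does not mention Cohort 1. The number applied is the expected number minus the missed doses recorded in the eCRF, and compliance is applied divided by expected.

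Footnote 3 of Listing 16.2.5.4 carries the same constant, but in its sentence on twice-daily dosing: "the expected number of IP applications for each subject is 30 (Cohort 1) or 170 (Cohort 2 BID"). Its once-daily sentence gives 85 for Cohort 2 and nothing for Cohort 1.

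**The schedule.** Protocol 4.12.2 states: "Subjects in Cohort 1 will be instructed to apply IP once daily (QD"). SAP 3.1 describes two weeks of once-daily treatment. Footnote i of SAP Table 1 puts the first dose on Day 1 and adds: "On Day 15 (last dose application), PK samples will be collected pre-dose". Footnote j of the Cohort 1 schedule in Protocol 1.3 says: "Clinic personnel will apply assigned IP on Visits 2, 4 and 5 (Baseline, Day 8 and Day 15").

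**Completion.** SAP 6.1.7 defines completing the study as "Completion of the primary efficacy assessment (IGA) at Week 12".

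**Weight.** SAP 6.1.7 takes returned tube weight minus dispensed tube weight. Footnote 1 of Table 14.1.6 says the opposite: "Total weight of IP is determined by subtracting returned tube weight from the dispensed tube weight".

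**The concern.** A fixed denominator should match the schedule it summarises, and 30 matches no Cohort 1 schedule in either document. The two places that state it also disagree on whether Cohort 1 is dosed once or twice daily.

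The numerator is built from the denominator, so a wrong constant does not simply cancel in the ratio. It also enters the reported exposure, in the row "Total Number of IP Applications" of Table 14.1.6. At stake are that row, the compliance categories in the same table, and the overall compliance percentage in Listing 16.2.5.4, all for Cohort 1. Protocol 2.3 calls this the first human study of the topical cream, so its exposure table should be right even though the cohort is small.

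The same block of derivations has two further problems. The sign of the weight formula affects both cohorts. The rule for how long the compliance period runs in Cohort 2 is stated in two ways.

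**Working it through.** **Inputs.** First dose Day 1 and last dose Day 15 for Cohort 1, with a window of 1 day either side of the Day 15 visit (SAP Table 1). Day 85 is the nominal Week 12 visit for Cohort 2 (SAP Table 2). The formula is that of SAP 6.1.7: k × (last − first + 1), with k = 1 for once daily and 2 for twice daily.

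**Reproducing the SAP's constants on nominal days**
- Cohort 2 once daily: 85 − 1 + 1 = 85. Agrees.
- Cohort 2 twice daily: 2 × 85 = 170. Agrees.
- Cohort 1 once daily: 15 − 1 + 1 = 15. The SAP says 30.

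With the visit window, Cohort 1 gives 14 to 16. The figure of 30 appears only with the twice-daily factor, 2 × 15 = 30. The documents do not say whether that is its origin. The Cohort 2 constants are nominal too: the Week 12 window of 7 days either side gives 78 to 92 once-daily applications.

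**Reported applications if 30 is used.** With no misses, 30 − 0 = 30 instead of 15. Over six such subjects the total is 6 × 30 = 180 instead of 6 × 15 = 90 (84 to 96 with the window).

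**Compliance if 30 is used**

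| Missed doses (m) | (30 − m)/30 | (15 − m)/15 |
|---|---|---|
| 0 | 100% | 100% |
| 3 | 90% | 80% |
| 4 | 87% | 73% |
| 5 | 83% | 67% |
| 6 | 80% | 60% |
| 7 | 77% | 53% |

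The 80% criterion then tolerates 6 misses (24/30) instead of 3 (12/15). Only subjects with 4, 5 or 6 misses change side. Staff apply 3 of the 15 doses, which leaves 12 at home, so 4 to 6 misses means 4/12 = 33% to 6/12 = 50% of home doses.

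**Weight.** If a tube loses g grams, returned minus dispensed is −g. SAP 6.1.7 therefore gives a negative amount for every used tube, and Table 14.1.6 a positive one.

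**Cohort 2 compliance period.** The compliance entry in SAP 6.1.7 ends the period at treatment completion or discontinuation. The expected-applications entries assign 85 or 170 to anyone who completes the study, meaning anyone with a Week 12 IGA. Protocol 4.8 and 4.9 separate stopping cream from leaving the study, and Protocol 4.6.1 has unblinded subjects stop treatment but stay in follow-up. One subject can therefore meet both rules. As an assumed illustration, take once-daily dosing, last application on Day 29, and a Week 12 IGA done:

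| Earlier misses | Actual period | Fixed 85, later doses not logged as missed | Fixed 85, later doses logged as missed |
|---|---|---|---|
| 0 | 29/29 = 100% | 85/85 = 100% | 29/85 = 34% |
| 8 | 21/29 = 72% | 77/85 = 91% | 21/85 = 25% |

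**The case against.** The strongest reply is that the 30 may never be used. Completion is defined by the Week 12 IGA, a visit Cohort 1 does not have, so read literally no Cohort 1 subject is assigned it. SAP 7.4 and Protocol 6.1.7 also say that application counts are summarised from diary data, and under Protocol 4.12.3 the diary records each dose. Table 14.1.6 separately reports grams used, and Listing 16.2.5.5.1 lists each missed once-daily dose. Neither depends on the 30.

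This stands as a limit on the consequence: doubled exposure is possible, not established. It does not rescue the text. The SAP does not say whether the diary or the derived count governs. The literal completion rule would also leave the Cohort 1 column of the Completed Study row in Table 14.1.1 at zero, and the listing footnote would still print 30 under the wrong frequency.

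It is also fair to say that few or no subjects may miss 4 to 6 of 15 doses, and that runs of more than three missed days already fail the separate consecutive-days rule in SAP 7.4. On Cohort 2, the result depends on eCRF practice and on an IP Handling Manual that is not among the documents, so only the inconsistency can be shown.

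**Conclusion.** Minor, and wrong as written. On the documents' own schedule the Cohort 1 expected count is 15 (14 to 16), half of the stated 30, and nothing in the documents explains the difference. If the constant is applied, reported applications for an adherent subject double, and the 80% criterion becomes too lenient for subjects with 4 to 6 misses. The effect is confined to descriptive Cohort 1 output in about 6 subjects. The reversed weight formula in SAP 6.1.7 is a plain error for both cohorts, already stated correctly in Table 14.1.6.

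Three stronger inferences are not supported:
- **That Cohort 1 was to be dosed twice daily.** The descriptions of its treatment say once daily; only the listing footnote implies otherwise.
- **That the 30 affects efficacy or the Per Protocol set.** That set is limited to Cohort 2 (SAP 5). Nor does the 30 enter the definition of an evaluable Cohort 1 subject, which rests on completing treatment and having the PK results (Protocol 4.2).
- **That Cohort 2 Per Protocol membership will be biased in a known direction.** The 80% criterion helps define that sensitivity set, but the number of subjects who stop cream and still have a Week 12 IGA is not given, nor is the way later doses are logged. The Per Protocol definition does not state the consecutive-days rule, so that rule cannot be relied on to remove such subjects. The ITT primary analysis is unaffected.

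**What to change.** - **Expected count.** Replace the Cohort 1 constant with the date formula already in SAP 6.1.7 (15 on the nominal schedule), under once-daily dosing, both there and in footnote 3 of Listing 16.2.5.4. The final dose is applied by staff at the Day 15 visit, so the last treatment date should be well documented for completers.
- **Completion.** Define Cohort 1 completion by its own visit schedule, not by the Week 12 IGA.
- **Source.** State whether the diary or the derived count feeds the applications row of Table 14.1.6.
- **Weight.** Define weight of product used as dispensed minus returned.
- **Cohort 2.** Before the blinded data review, reconcile the compliance period with the fixed 85 or 170 and with the IP Handling Manual. One stated denominator should serve the 80% criterion, and doses after stopping should never count as applied. Whether it covers the actual or the planned treatment period is for the sponsor to choose and justify.

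The cost is SAP wording, one footnote and programming. No new data are needed and the dosing schedule does not change.

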4.12.3 Treatment Compliance

Each IP tube will be weighed prior to dispensing at the Baseline visit and at each follow-up clinic visit according to the Schedule of Visits and Assessments ([Section 1.3](#)). When IP is applied in the clinic, the IP tube will be weighed before and after IP application. If the subject's actual use is substantially different than the expected use (see IP Handling Plan), the subject will be retrained on the investigational product application technique.

Subjects will complete a daily diary recording the date and time of each dose applied, any missed doses, and a comment section should the subjects have a comment, e.g., record potential AEs, handwashing or use of hand sanitizer within 4 hours. Site personnel will review the diaries and use the information to question the subject regarding compliance and AEs and then record appropriate information in source documents and complete CRFs. If a subject misses a dose, they should be instructed to return to the protocol investigational product administration schedule (i.e., if subject forgets a dose they should wait until the next planned application and apply as usual).

A subject will be considered compliant with the dosing regimen if the subject applies at least 80% of the expected applications during the investigational product application period and does not miss more than 3 consecutive doses.

Compliance will be assessed by review of the dosing diary. Weight of investigational product applied will be measured for reporting purposes.

If the diary shows less than 80% of expected use, the subject is using too little investigational product and retraining must be conducted and documented.

Compliance will be documented in source and in CRF.

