#### **7.4. Exposure and Compliance**

The number of IP applications by each subject based on diary data will be summarized using descriptive statistics appropriate for continuous variables.

The amount of IP each subject used based on tube weight will be summarized descriptively by treatment group using continuous methods.

A subject will be considered compliant with the dosing regimen if the subject applies at least 80% of the expected applications during the IP application period and does not miss more than 3 consecutive days of dosing.

Investigational product application compliance will be calculated based on number of applications divided by the expected number of IP applications. Compliance will be summarized descriptively by treatment group using the following categories:

- >100%
- ≥80% - ≤100%
- <80%

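### The SAP derives grams used with the opposite sign to its own table footnote, and derives applications so that compliance above 100% cannot occur

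*SAP*

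**What the plan says.** **Weight.** SAP 6.1.7 (Derived Variables) gives Weight of IP (g) as "returned tube weight – dispensed tube weight". The Table 14.1.6 shell reports total grams applied by arm (mean, SD, median, minimum, maximum), and its footnote [1] reads: "Total weight of IP is determined by subtracting returned tube weight from the dispensed tube weight". The two subtractions run in opposite directions.

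**Applications and compliance.** SAP 6.1.7 derives the number of applications as "number of expected IP applications – missed IP applications as collected in the electronic case report form (eCRF"), and the footnote to Listing 16.2.5.4 repeats this. Compliance in SAP 7.4 is "number of applications divided by the expected number of IP applications". For Cohort 2 the denominator is "170 (Cohort 2 BID) for subjects who complete the study", and 85 for once-daily completers. For early discontinuers it is treatment days multiplied by daily frequency. SAP 7.4 then states: "Compliance will be summarized descriptively by treatment group using the following categories". The first category listed is above 100%, and Table 14.1.6 carries the same row.

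**Source data.** Protocol 4.12.3 says: "Subjects will complete a daily diary recording the date and time of each dose applied, any missed doses". Protocol 6.1.7 and SAP 7.4 both base the application count on the diary. The compliance entry in SAP 6.1.7 instead names drug accountability data, and the application formula uses missed doses from the eCRF. SAP section 10 logs a change to the consecutive-missed-dose rule but does not mention how applications are counted.

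**The concern.** A programmer working from SAP 6.1.7 and one working from the table footnote would deliver opposite signs for the same variable. Followed literally, 6.1.7 puts negative grams applied in the exposure table, exchanges minimum and maximum, and ranks heavier use below lighter use.

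The compliance problem is structural. The plan offers a category for subjects who applied more than expected, then derives the numerator so that no subject can fall in it. A reader of the study report who sees zero in that row for every arm would naturally conclude that over-application did not happen. Subjects know whether they are assigned once- or twice-daily use (Protocol 4.6), so extra applications in the once-daily arms are plausible and worth being able to describe.

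**Working it through.** **1. Reproduce the plan's denominators.** Expected applications = (last day − first day + 1) × applications per day. Day 1 to Day 85 gives 85 × 1 = 85 once daily and 85 × 2 = 170 twice daily, both as stated in SAP 6.1.7. The Cohort 1 once-daily figure of 30 does not reproduce this way: Day 1 to Day 15 gives 15, and Listing 16.2.5.4 puts the 30 under twice-daily dosing. Those two places need reconciling separately, and the result in step 3 does not depend on the figure.

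**2. Sign of the weight.** Take a tube dispensed at 12 g and returned at 5 g.
- SAP 6.1.7: 5 − 12 = −7 g.
- Table 14.1.6 footnote [1]: 12 − 5 = +7 g.

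The magnitude is the same and only the sign differs. An unused tube gives 0 under both.

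**3. Ceiling on compliance.** With E expected and M ≥ 0 missed, compliance = (E − M)/E = 1 − M/E ≤ 1. Enumerating every E from 1 to 170 and every M from 0 to E gives a maximum of exactly 1.000. This covers completers and early discontinuers alike.

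**4. What the derivation hides.** All cases below are completers with no missed dose recorded.

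| Case | Applied / expected | Count-based | SAP 6.1.7 |
|---|---|---|---|
| QD, 10 extra applications | 95/85 | 111.8% | 100% |
| QD, applying twice daily | 170/85 | 200% | 100% |
| QD or BID, applying through Day 92 | 92/85 or 184/170 | 108.2% | 100% |
| QD or BID, last application Day 78 | 78/85 or 156/170 | 91.8% | 100% |

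Days 78 and 92 are the ends of the Week 12 visit window (Day 85 ± 7). The third row shows that values above 100% would arise from ordinary visit timing alone. The last row shows that the fixed denominator conceals shortfall in the same way.

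**5. Illustrative size in grams.** This step rests on an assumption. Protocol 2.4.1 gives about 1.5 mg of drug per once-daily application of the 0.3% cream, so 1.5 mg / 0.003 = 500 mg, or 0.5 g of cream. Over 85 days that is 85 × 0.5 = 42.5 g once daily and 170 × 0.5 = 85 g twice daily. SAP 6.1.7 would show −42.5 g and −85 g. If the true amount were half or double that (0.25 to 1.0 g), the totals would be 21.25 to 85 g once daily and 42.5 to 170 g twice daily. The sign is wrong at any value.

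**The case against.** The best reply is that these are editorial slips in descriptive output, and that the more serious consequences a reader might infer do not follow. Most of that reply stands.

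- **Over-use would be undetectable.** It would not. Table 14.1.6 reports grams by arm with minimum and maximum, and a reversed sign keeps the magnitude. Listing 16.2.5.1 shows the applied dose in grams for in-clinic applications, Listing 16.2.5.2 shows dispensed and returned weights per tube, and Listing 16.2.5.4 shows CRF compliance by visit. Tubes are also weighed during the trial, and subjects whose use departs substantially from expectation are retrained (Protocol 4.12.2 and 4.12.3). The ceiling is exact only for the derived application count and the compliance percentage.
- **Over-users are wrongly kept in the Per-Protocol set because of the formula.** They are not. The Per-Protocol definition (SAP section 5) and the compliance rule (SAP 7.4) set a floor of 80% and no upper limit, so a subject recounted at 200% still passes. Exclusion for over-use would come through important protocol deviations, with population assignment confirmed at a blinded data review. The formula does not touch that route.
- **A QD-versus-BID or 0.1%-versus-0.3% test is compromised.** No such test is planned. All five comparisons in SAP 4.1, 8.1.1 and 8.2 set active cream against pooled vehicle, and the primary analysis is ITT under a treatment-policy strategy. Neither derived variable enters an inferential model.

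It can also fairly be said that the footnote already has the correct subtraction, that eCRF missed doses probably come from the diary, and that the planned listings do not show that home doses applied were entered in the database. None of this removes the contradiction on sign or makes the over-100% row attainable.

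**Conclusion.** Both defects stand as written. SAP 6.1.7 and Table 14.1.6 footnote [1] give opposite signs for grams used, and the over-100% category is zero in every arm whatever subjects did. They follow from the text and from M ≥ 0, with no further assumption.

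The reach is limited to the descriptive exposure and compliance summary. The documents do not support saying that over-application leaves no trace, that Per-Protocol membership changes on compliance grounds, or that any planned efficacy comparison is affected. The practical risk is a published exposure table with negative grams and a zero row read as a finding. The gram totals in the working are illustrative only: they are back-calculated from an approximate dose rationale, and the expected use itself is defined in the IP Handling Plan, which is not among the documents reviewed.

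**What to change.** 1. In SAP 6.1.7, set Weight of IP (g) = dispensed tube weight − returned tube weight, to agree with Table 14.1.6.
2. If doses applied are in the database, count applications from the diary's dose-applied entries, as Protocol 6.1.7 and SAP 7.4 intend, and change the footnote to Listing 16.2.5.4 to match.
3. If only missed doses are in the database, delete the over-100% row from SAP 7.4 and Table 14.1.6, and state that the derived compliance cannot show over-application. Assess over-use from grams used against the expected use in the IP Handling Plan for the assigned frequency.
4. In either case, name one data source for compliance in SAP 6.1.7 and 7.4.

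Item 1 costs one line of SAP text, and item 3 costs SAP wording and minor programming. Item 2 is equally cheap only if home doses applied were entered, so that should be checked before choosing between 2 and 3. Item 3 also requires confirming that the IP Handling Plan states an expected weight.
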